8.10.2. Clinical Laboratory Evaluations

Laboratory test results (hematology and serum chemistry) at each scheduled visit and change from baseline will be summarized by treatment group.

Laboratory data will be tabulated using counts and percentages based on the following result class by each scheduled visit and treatment group.

- Normal: result is within the local lab normal range
- Abnormal: result is either higher or lower than the normal range

The number and percentage of subjects with the following potentially clinically significant (PCS) abnormal liver function tests will be summarized:

- ALT $\geq 3 \times$ ULN
- AST $\geq 3 \times$ ULN
- ALT or AST $\geq 3 \times$ ULN
- Total bilirubin $\geq 1.5 \times$ ULN and $\geq 2 \times$ ULN
- ALP $\geq 1.5 \times$ ULN and $\geq 3 \times$ ULN
- ALT or AST $\geq 3 \times$ ULN and Total bilirubin $\geq 2 \times$ ULN
- Potential Hy's Law cases: ALT or AST $\geq 3 \times$ ULN, Total bilirubin $\geq 2 \times$ ULN, and ALP $\leq 2 \times$ ULN

A listing of patients with any post baseline abnormal liver function tests will be presented.

All clinical laboratory data will be listed. Values outside the normal ranges will be flagged.

8.10.3. 12-Lead ECG

Descriptive statistics will be provided for 12-lead ECG findings (PR, QRS, QT, and RR) and changes from baseline for each scheduled visit.

All abnormal values will be assessed for clinical significance; clinical significance will be captured in the case report form. Number and percent of subjects within each result class (normal, abnormal but not clinically significant, and abnormal and clinically significant) will be presented by time point and treatment group.

Shift tables will be used to summarize individual subject changes from baseline to each post baseline time point using the following categories; normal, abnormal but not clinically significant, and abnormal and clinically significant.

All 12-lead ECG findings will be listed by subject.

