6. STUDY ENDPOINTS

6.1. Safety Endpoints

The safety and tolerability of locally administered MBN-101 will be assessed by:

- Treatment-emergent adverse events.
- Treatment-emergent serious adverse events.
- Changes in clinical laboratory tests (clinical chemistry, hematology, and urinalysis).

- Changes in vital signs (blood pressure, pulse, respiratory rate and body temperature).
- Changes in physical exams.
- Clinical findings of 12-lead electrocardiograms.

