8.10.4. Vital Signs

Descriptive statistics will be provided for the vital signs (blood pressure, pulse, respiratory rate, and temperature) and changes from baseline for each scheduled visit.

Vital sign results will also be tabulated based on the following result class.

- Normal: result is within the normal range
- Abnormal: result is either higher or lower than the normal range

All abnormal values will be assessed for clinical significance; clinical significance will be captured in the case report form. Number and percent of subjects within each result class (normal, abnormal but not clinically significant, and abnormal and clinically significant) will be presented by time point and treatment group.

Additionally, shift tables, showing individual subject changes from baseline to each post baseline time point, by treatment group, will be presented for each vital sign parameter using the following categories: normal, abnormal but not clinically significant, and abnormal and clinically significant.

A listing of all vital signs will be provided by subject.

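### The summary laboratory tables show neither the direction of an abnormality nor its shift from baseline, although the endpoint is change and three other safety domains get shift tables

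*SAP*

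**What the plan says.** Section 6.1 names the laboratory safety endpoint as "Changes in clinical laboratory tests (clinical chemistry, hematology, and urinalysis"). Section 8.10.2 then plans these outputs:

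- **Continuous summary:** "Laboratory test results (hematology and serum chemistry) at each scheduled visit and change from baseline will be summarized by treatment group". Under section 8.1 this means n, mean, SD, median, minimum and maximum.
- **Categorical summary:** "Laboratory data will be tabulated using counts and percentages based on the following result class by each scheduled visit and treatment group". The two classes are "Normal: result is within the local lab normal range" and "Abnormal: result is either higher or lower than the normal range".
- **Liver tests:** "The number and percentage of subjects with the following potentially clinically significant (PCS) abnormal liver function tests will be summarized". The list covers multiples of the upper limit of normal for ALT, AST, total bilirubin and ALP, and potential Hy's Law cases. In addition, "A listing of patients with any post baseline abnormal liver function tests will be presented".
- **Listings:** all laboratory data, with out-of-range values flagged.

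No laboratory shift table is planned. For vital signs, section 8.10.4 starts from the same two classes but goes further: "Additionally, shift tables, showing individual subject changes from baseline to each post baseline time point, by treatment group, will be presented" for each parameter. Sections 8.10.3 (ECG) and 8.10.5 (physical examination) also plan shift tables.

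**The concern.** A per-visit count of abnormal results is not a measure of change. A subject who was out of range before dosing counts the same as one who went out of range after it. A subject who moves from above the range to below it counts as abnormal both times, and so appears unchanged. For white cells, platelets or potassium, direction is a large part of the safety meaning.

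Safety and tolerability is the primary objective (section 2.1), and subjects enrol with a bone or fracture-site infection and undergo surgery (section 3.1). It is reasonable to assume that out-of-range baseline values will be common, although the SAP gives no rate. The adverse-event definition in section 8.10.1 separates new or worsened events from pre-existing ones. The laboratory class table makes no such separation, and the SAP gives no reason for treating laboratory tests differently from the three neighbouring domains.

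**Working it through.** The SAP gives no figure on this point, so there is none to reproduce. The check asks what the planned class table can determine, and then what the other planned outputs add.

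**1. What per-visit counts determine.** Take n subjects with values at both times, b abnormal at baseline, f abnormal at follow-up and k abnormal at both. Newly abnormal subjects number f − k. Since k lies between max(0, b + f − n) and min(b, f), the number newly abnormal lies between max(0, f − b) and min(f, n − b).

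Group sizes come from section 8.1: 6 per dose, 18 active combined. The abnormal counts below are assumed.

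| n | b | f | Lower: max(0, f − b) | Upper: min(f, n − b) |
|---|---|---|---|---|
| 6 | 3 | 3 | 0 | 3 |
| 6 | 2 | 3 | 1 | 3 |
| 6 | 1 | 1 | 0 | 1 |
| 6 | 0 | 2 | 2 | 2 |
| 18 | 9 | 9 | 0 | 9 |
| 18 | 6 | 9 | 3 | 9 |
| 18 | 0 | 6 | 6 | 6 |

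The count is exact when nobody is abnormal at baseline, and widest when half are abnormal at both times. These bounds concern only normal against abnormal. A high-to-low crossing is not counted as new in any row, and no row gives direction.

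**2. What the other outputs add.**

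- *Change from baseline.* In a group of 6, the minimum and maximum change show the largest individual fall and rise, with sign. They do not show whether a value crossed its range: the same rise can bring a low value into range or take a normal value out of it. All tests are run at local laboratories (section 5.3.2) in a multi-center study (section 3.1). If ranges differ by site, pooled raw changes say still less about crossings. The sentence that plans this summary names hematology and serum chemistry, not urinalysis, which is part of the endpoint.
- *Liver thresholds.* Section 5.3.2 lists 13 hematology and 19 chemistry analytes, 13 + 19 = 32. The thresholds cover 4 of them. They give direction, but the counts are not stated to be limited to post-baseline or newly occurring values.
- *Listings.* These hold the full answer. Table 1 schedules hematology and chemistry at five time points (screening, Hour 48, Weeks 2, 6 and 12), apart from early termination. With 24 subjects that is up to 24 × 32 × 5 = 3,840 values to cross-check by hand.

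**The case against.** The strongest reply is that nothing is lost. All values are listed and flagged, there are only 24 planned subjects, and a reader can follow each one from baseline with its direction. Minimum and maximum change would bring out a marked creatinine rise or platelet fall. The liver thresholds are directional. The randomized pooled placebo group stands beside each dose in the same tables, so disease and surgical background is visible. CRP and ESR are handled separately in section 8.9.9, with change from baseline and clinical-significance classes. Safety analysis is descriptive only.

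Most of this stands, and it rules out stronger readings. A reader might infer that new abnormalities cannot be identified at all, or that renal, hematological and coagulation signals are hidden. The listings and change summaries contradict that. A reader might also infer that dose escalation is compromised. The DRC Charter says that the committee works from raw listings, including out-of-range laboratory values, and receives no aggregate data. Nor do the documents show that abnormal counts would reflect the disease more than the product: they give no baseline rate, and placebo is shown alongside.

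It is also fair that the existing shift tables use clinical-significance classes, not low / normal / high. The comparison with ECG and vital signs supports having a shift table; the directional classes rest on the merging of high and low in section 8.10.2 itself.

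What the reply does not do is put new abnormalities, or their direction, into a summary table for most analytes.

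**Conclusion.** The point holds as a weakness in how the laboratory part of the primary safety objective is summarized. The class table merges directions and ignores baseline, so in general it does not give the number or direction of new abnormalities. Outside the liver-threshold counts and the minimum and maximum changes, that information is available only from the flagged listings.

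Its size depends on how many subjects are out of range at baseline, which the SAP does not state. Under the assumed counts above, the uncertainty in a 6-subject group runs from none (no abnormal baselines) to 0 to 3 subjects (half abnormal at both times). In the combined active group it can reach 0 to 9 of 18. The bounds assume that every subject has a value at both times.

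The consequence is limited to the clarity of the final report. No sample size, error rate or escalation decision depends on it. The change is still worth making, because the inconsistency lies within one section of the SAP and is cheap to remove.

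**What to change.** In section 8.10.2:

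- Replace the two classes by low / normal / high against the local range for each hematology and serum chemistry analyte. Keep normal / abnormal for qualitative urinalysis, and name urinalysis explicitly among the tests summarized.
- Add shift tables by treatment group from baseline to each scheduled visit, and from baseline to the worst post-baseline value. Show the lowest and the highest value separately, so that a subject who moves in both directions is seen in both.
- State whether the liver-threshold counts refer to post-baseline values, and show them by baseline status.

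The cost is a few more standard tables and their programming. Baseline is already defined in section 8.3, pre-dose samples are already scheduled in Table 1, and the planned two-class table already needs the local ranges. No new data are collected.

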8.10.4. Vital Signs

Descriptive statistics will be provided for the vital signs (blood pressure, pulse, respiratory rate, and temperature) and changes from baseline for each scheduled visit.

Vital sign results will also be tabulated based on the following result class.

- Normal: result is within the normal range
- Abnormal: result is either higher or lower than the normal range

All abnormal values will be assessed for clinical significance; clinical significance will be captured in the case report form. Number and percent of subjects within each result class (normal, abnormal but not clinically significant, and abnormal and clinically significant) will be presented by time point and treatment group.

Additionally, shift tables, showing individual subject changes from baseline to each post baseline time point, by treatment group, will be presented for each vital sign parameter using the following categories: normal, abnormal but not clinically significant, and abnormal and clinically significant.

A listing of all vital signs will be provided by subject.

8.10.5. Physical Examination

Shift tables for physical examination overall assessment will be used to summarize individual subject changes from baseline to each post baseline time point using the following categories; normal, abnormal but not clinically significant, and abnormal and clinically significant.

Physical examination findings will be listed by subject.

8.11. Pharmacokinetic Analysis

Bismuth (Bi) concentration data will be analyzed by noncompartmental analysis (NCA) with Phoenix™ WinNonlin® Version 6.4 or higher, using an extravascular administration model

SAP MBN-101-201
Version 1.0, 19 July 2018

and actual sampling times. The PK parameters will be calculated and analyzed by another vendor and reported separately.

Summary statistics [N, mean, standard deviation (SD), minimum (Min), median (Med), maximum (Max), percent coefficient of variability (% CV)] for the PK concentration data will be presented by treatment group and time point.

A listing of the PK concentrations by subject will be provided.

rg kg

Interim Analysis are planned for this study for the purpose of DRC. The purpose of the interim analysis is to allow the DRC to review the data and to make recommendation to the Sponsor on whether or not the next cohort of the subjects should be studied as planned.

Data Review Committee (DRC) Charter

A Phase 2a Randomized, Single-Blind, Placebo-Controlled, 24-week Escalating Dose Study to Assess the Safety, Tolerability and Clinical Activity of 3 Concentrations of Locally Applied MBN-101 to Infected Osteosynthesis Sites

Protocol Number: MBN-101-201

Sponsor of Protocol: Microbion Corporation

Date of Document: 28 April 2015

Version: 1.0

TABLE OF CONTENTS

TABLE OF CONTENTS.....	2
REVISION HISTORY OF THE DOCUMENT	4
INTRODUCTION	4
PRIMARY RESPONSIBILITIES OF THE DRC	4
Safety Monitoring	4
Efficacy Data and Interim Analyses	5
Publications.....	5
Confidentiality	5
MEMBERSHIP OF THE DRC	5
Members	5
Contact List.....	5
Role of the DRC Members	6
Role of the DRC Chair.....	6
Sponsor	6
CONFLICTS OF INTEREST	7
TIMING AND PURPOSE OF THE DRC MEETINGS.....	7
DRC Quorum.....	7
Types of DRC Meetings	7
Schedule of Meetings.....	7
Voting	7
Orientation Meeting	7
Masking Policy	7
Contract Research Organization/Data Analysis Center	8
Formal Interim Analysis Meetings	8
PROCEDURES TO ENSURE CONFIDENTIALITY & PROPER COMMUNICATION.....	8
Open and Closed Sessions	8
Minutes of the DRC Meeting.....	8
Retention of DRC Minutes	8
Recommendations to the Sponsor.....	8
STATISTICAL MONITORING GUIDELINES.....	8

CONTENT OF THE DRC'S OPEN AND CLOSED REPORTS	8
RESIGNATION, TERMINATION AND REPLACEMENT OF DRC MEMBERS.....	8
TABLES/LISTINGS TO BE REVIEWED DURING DRC MEETINGS.....	9
Administrative Data	9
Data Listings	9
Efficacy Data	10

REVISION HISTORY OF THE DOCUMENT

The DRC Charter is currently in Version 1.0. (A Chair will be selected, and upon specification, the Version will be revised to Version 1.1).

INTRODUCTION

This Charter is for the Data Review Committee (DRC) for protocol MBN-101-201 titled **A Phase 2a Randomized, Single-Blind, Placebo-Controlled, 24 week Escalating Dose Study to Assess the Safety, Tolerability and Clinical Activity of 3 Concentrations of Locally Applied MBN-101 to Infected Osteosynthesis Sites.**

This Charter defines the scope, roles and responsibilities, operating procedures, and membership of the DRC. The DRC membership consists of independent medical experts with expertise relevant to the proposed clinical indication.

PRIMARY RESPONSIBILITIES OF THE DRC

The primary responsibility of the DRC is to protect the safety of trial participants.

The DRC will serve in an advisory capacity to the Sponsor. The DRC may make recommendations to the Sponsor regarding:

- Continuation of the trial without modification.
- Continuation of the trial with modification to the Protocol, Informed Consent and/or Investigator's Brochure.
- Suspension or termination of patient enrollment.
- Termination of the trial.

The DRC will be responsible for written documentation including the rationale of any recommendations. In all situations, the final decision to act upon any DRC recommendation will rest with the Sponsor.

In order to execute its responsibilities, the DRC membership will have read and be familiar with the Protocol, Investigator's Brochure, Informed Consent, and Safety Monitoring Plan. The DRC membership will also have read and approved this Charter.

Safety Monitoring

The DRC will exercise its primary responsibility by the periodic review of accumulating study data including: trial recruitment, retention, and safety data. Additional DRC responsibilities include:

- 1) Dose escalation recommendations – determining when subjects may be enrolled into the next higher dose cohort.
- 2) Recommendations regarding re-starting enrollment should the threshold of the protocol stopping rules be reached.

Efficacy Data and Interim Analyses

The DRC will not be responsible for reviewing efficacy data or making recommendations on the basis of efficacy since the trial's primary objective is safety. Since the study is not adequately powered for statistical tests of hypotheses, no formal statistical interim analysis of efficacy data is planned. However, the DRC may request to review ongoing efficacy data from the study in an effort to better understand the evolving benefit/risk relationship of the investigational product in the proposed indication.

Publications

The DRC will not have any special role in publications resulting from the study.

Confidentiality

All materials, discussions and proceedings of the DRC are considered confidential. The DRC membership will protect the integrity of the trial by maintaining confidentiality regarding the trial data and trial execution. All DRC members will be held to the same confidentiality requirements. Any communication of confidential information outside of the DRC will be fully documented.

MEMBERSHIP OF THE DRC

Members

The DRC is a multidisciplinary group consisting of three voting members. All three members are independent of the Sponsor and the clinical trial. At least one member is an infectious diseases specialist.

Contact List

DRC Member #1: Redacted

DRC Member #2: Redacted

DRC Member #3: Redacted

Role of the DRC Members

- Protect the safety of study participants.
- Review and be familiar with the protocol, informed consent, investigator's brochure, and the safety monitoring plan, as well as any amendments to these documents.
- Review and approve the DRC charter.
- Participate in DRC meetings and review any materials provided.
- Evaluate the accumulating safety data on a regular periodic basis as well as an *ad hoc* basis. It is anticipated that the DRC will hold formal meetings via teleconference approximately 4-5 times over the course of the study.
- Review study performance including recruitment, accrual and other factors that might be relevant to study safety.
- Engage in open debate and discussion.
- Make recommendations to the Sponsor regarding study conduct.
- Ensure the confidentiality of the study data.
- Discharge itself from its duties when the study is complete.

Role of the DRC Chair

The DRC Chair will be appointed by the Sponsor and the CRO. The DRC Chair will be responsible for:

- Co-chairing the DRC Orientation meeting.
- Preparing the DRC agendas.
- Chairing and facilitating the DRC meetings.
- Reviewing Serious Adverse Events (SAEs) and Adverse Events of Special Interest (AESI) on an ongoing basis to determine if an ad hoc meeting of the DRC is required.
- Scheduling ad hoc DRC meetings.
- Scheduling DRC meetings at milestone time points such as dose cohort escalation decisions.
- Ensuring that attendance of the full DRC membership is present at each DRC meeting.
- Reviewing DRC minutes prior to release to the general DRC membership for approval.
- Ensuring the DRC minutes are reviewed and approved by the DRC membership.
- Serving as the lead liaison between the DRC and the Sponsor.
- Ensuring that any DRC recommendations to the Sponsor are made in a timely manner.

Sponsor

The Sponsor is responsible for:

- Choosing the DRC membership.
- Appointing the DRC Chair.
- Scheduling and Co-Chairing the Orientation Meeting.
- Ensuring that the DRC has the information needed to execute its responsibilities.
- Responding to the DRC in a timely manner with regard to any DRC recommendations, questions, or requests.
- Informing the DRC in a timely manner of any changes to the clinical protocol, informed consent, Investigator Brochure or any other relevant regulatory documents related to the clinical trial.

CONFLICTS OF INTEREST

The DRC membership consists of independent medical experts. Any member reporting or developing a conflict of interest during the course of the clinical trial will report this conflict to the DRC Chair and the Sponsor such that a replacement member of the DRC may be identified and established with minimal disruption to the roles and responsibilities of the DRC.

TIMING AND PURPOSE OF THE DRC MEETINGS

The DRC will determine the schedule and timing of its meetings at its Orientation Meeting. This Charter will be amended at that time.

The purpose of the DRC meetings will include the general review of safety data. Meetings of the DRC need not be face-to-face. It is anticipated that DRC meetings will be conducted via conference call, and the group will meet approximately 4-5 times during the conduct of the study.

DRC Quorum

The presence and participation of all three DRC voting members will be considered a quorum. At any particular meeting, a DRC quorum will be considered necessary and sufficient to conduct DRC business.

Types of DRC Meetings

It is anticipated that all DRC meetings will consist of an open session followed by a closed session followed by a second open session. During this second open session, recommendations of the DRC will be made directly to the Sponsor or Sponsor's representative.

Schedule of Meetings

The DRC will determine the schedule and timing of its meetings at its Orientation Meeting. In general, the DRC will meet for the following purposes:

- Milestone meetings required to trigger specific protocol events such as dose cohort escalation.
- Ad hoc meetings called by the DRC Chair, any DRC member, the Sponsor, or the Study Team.

Voting

All members of the DRC will be considered voting members.

Orientation Meeting

The DRC Chair will schedule an Orientation meeting which will be co-chaired by both the DRC Chair and the Sponsor. The purpose of the orientation meeting is to:

- Introduce and enable Q & A between the DRC, Sponsor and Study Team Members.
- Review the development program and proposed clinical trial for MBN-101.
- Discuss, approve and amend the DRC Charter.
- Outline DRC operating procedures and expectations.

Masking Policy

The DRC will review unblinded data. The DRC will exercise caution when providing recommendations to or otherwise communicating with the sponsor not to provide any recommendations or communications that might result in unblinding of the sponsor to the any data from the clinical trial.

Contract Research Organization/Data Analysis Center

The Contract Research Organization will be responsible for:

- Providing the necessary data listings and administrative information for each DRC data review meeting.
- Facilitating SAE and AESI review by the DRC Chair as these events occur.
- Providing additional information as requested by the DRC and approved by the Sponsor.

Formal Interim Analysis Meetings

No statistical interim analyses will be conducted. The study is expected to continue until its completion barring any unforeseen safety issue.

PROCEDURES TO ENSURE CONFIDENTIALITY & PROPER COMMUNICATION

Open and Closed Sessions

It is anticipated that all DRC meetings will consist of an open session followed by a closed session followed by a second open session. During this second open session, recommendations of the DRC will be made directly to the Sponsor or Sponsor's representative.

Minutes of the DRC Meeting

The DRC will generate both open and closed session minutes for each meeting. The DRC Chair will be responsible for transferring the DRC closed session meeting minutes to a secured server provided by the CRO to ensure confidentiality until completion of the study. The DRC Chair will also be responsible for providing open session minutes to both the Sponsor and the CRO as soon as they are available. DRC open and closed session minutes should be distributed to and approved by the DRC membership within 3 working days of the DRC meeting.

Retention of DRC Minutes

Minutes recorded from DRC meeting will be retained as long as the study data is retained.

Recommendations to the Sponsor

The DRC will make recommendations to the Sponsor orally during the open session and in writing.

STATISTICAL MONITORING GUIDELINES

CONTENT OF THE DRC'S OPEN AND CLOSED REPORTS

Given the exploratory nature and small sample size of the current Phase 2a trial, there are no statistical monitoring guidelines considered. The protocol does have stopping rules based on clinical guidelines which will be monitored throughout the study.

RESIGNATION, TERMINATION AND REPLACEMENT OF DRC MEMBERS

It is anticipated that DRC members will continue their membership until the study is completed and the DRC is discharged. However, in the event that a DRC member must be replaced, the DRC Chair should be notified of the pending departure and notify the Sponsor and other DRC members. The replacement of the DRC member will be at the discretion of the Sponsor.

TABLES/LISTINGS TO BE REVIEWED DURING DRC MEETINGS

The DRC will be provided with raw data listings for review directly from the Clinical Trial Database (CTDB). Aggregate data will not be provided. As the DRC will be reviewing safety data on an accumulating basis, it is recognized that the data will be a mix of “clean” and “dirty” data residing in the CTDB at any given time. All “dirty” data will be cleaned and available to the DRC for all subsequent meetings.

Administrative Data

The Contract Research Organization will provide a summary of the following information for each data review meeting:

- The number of subjects failing screening.
- The number of subjects enrolled.
- The amount of follow-up time for subjects enrolled.
- The amount of data entered into the Clinical Trial Database.
- The amount of data “cleaned”.
- Date of last coding of AEs and Con Meds.
- The cutoff date corresponding to the data listings provided to the DRC. For example, all data entered into the CTDB as of a certain date.

Data Listings

The following data listings will be provided. For each data listing the repeating key subject information should be provided.

- Medical History
- Surgical History
- Eligibility/Exclusion Deviations
- Physical Exam including surgical site exam
- Vital Signs
- Adverse Events
- Serious Adverse Events
- Concomitant Medications, including concomitant antibiotics and pain medications
- Labs – Out of Range Values Only
 - Hematology
 - Serum Chemistry
 - Serologies
 - Urinalysis

Efficacy Data

If requested by the DRC, line listings of the number of treatment failures, serious interventions, readmissions and/or reoperations, as well as microbiology, radiographic and serologic marker analyses, will be provided.

Signature page redacted

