Patients will be randomized 3:1 (active:control) to three successive doses (0.025, 0.075, or 0.25 mg/mL w:v) of MBN-101 (up to 8 mL, for a dose of up to 0.2, 0.6, or 2.0 mg, respectively) or placebo (diluent). Enrollment to the next dose cohort will not commence until an evaluation by the Data Review Committee (DRC) of all available safety data on all patients through Week 6 of study supports escalation to the next cohort.

PK assessments will be performed predose and at nominal 1, 6, 12, 24, 36, 48 (Day 2), 60, 72 (Day 3), 96 (Day 4), and 336 (Day 14; Week 2) hours after administration of study drug.

Patients will undergo study visits at Hour 48 and Weeks 2, 6 and 12. All patients will be followed for a total of 12 weeks after surgery.

I kg **P**

Twenty-four adult male or female patients meeting protocol-specified eligibility criteria may participate in the study, with the objective of having a total of 6 patients per dose level in the MBN-101-treated group and 6 patients in a pooled placebo-treated group.

I g g

Subjects will be randomized in a 3:1 (active:placebo) ratio up to 24 hours prior to surgery via a central randomization scheme.

I g g

This study is a single blind study; however, knowledge of treatment assignment should remain limited to those directly involved with the patient's surgical procedure and other individuals on a need to know basis. In order to provide unblinding data in an emergency in the absence of an individual privy to treatment assignment, sites will be provided with a numbered unblinding envelope corresponding to each numbered test kit the site is delivered. These envelopes will be securely stored in the pharmacy. The unblinding envelope specifies the treatment group of the kit and should only be opened when absolutely necessary. For treatment of adverse events, it should be assumed that the patient has received study drug, thus avoiding the need to unblind the patient. However, in the event the Investigator determines the randomization assignment information is required to treat the patient for an adverse event, the Medical Monitor should be contacted. If the Medical Monitor cannot be reached, the blind may be broken by opening the envelope. The site should document the unblinding process in the patient's source documents.

I g g **P**

[Table 1](#) presents the schedule of events of the study.

Table 1. Schedule of Events

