5.3.3. Vital Signs

Vital signs include blood pressure, pulse, respiratory rate and body temperature; vital signs will be assessed according to the [schedule](#).

5.3.4. 12-Lead ECG

Testing will be conducted at screening, baseline, and 48 hours. The ECG trace will be stored at the investigational sites as source document; clinical interpretation, including normal, abnormal but not clinically significant, and abnormal and clinically significant, will be determined by the investigator.

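### The DRC charter's default listings leave out 12-lead ECG, the only safety endpoint group in SAP section 6.1 without one, although escalation rests on all available safety data

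*SAP*

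**What the plan says.** SAP section 3.1 does not open the next cohort until a DRC evaluation "of all available safety data on all patients through Week 6 of study supports escalation to the next cohort". Section 6.1 names six groups of safety endpoints, the last being "Clinical findings of 12-lead electrocardiograms".

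On timing, section 5.3.4 says: "Testing will be conducted at screening, baseline, and 48 hours". Table 1 also marks an ECG at Week 12 and at early termination or treatment failure. Section 8.10.3 plans summaries of PR, QRS, QT and RR with change from baseline, has clinical significance recorded on the case report form, and adds: "All 12-lead ECG findings will be listed by subject".

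The DRC charter (Version 1.0, 28 April 2015) follows in the same document as the SAP (Version 1.0, 19 July 2018). Its part on tables and listings has the DRC work from raw listings and states: "Aggregate data will not be provided". Under Data Listings it says: "The following data listings will be provided. For each data listing the repeating key subject information should be provided". It then names medical and surgical history, eligibility deviations, physical exam with surgical site exam, vital signs, adverse events, serious adverse events, concomitant medications, and out-of-range laboratory values. ECG is not named. Nor is it among the items offered on request under Efficacy Data, which are efficacy, microbiology, radiographic and serologic results.

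**The concern.** The escalation rule and the charter's list do not match. The rule asks for all available safety data; the list leaves out one of the SAP's own safety endpoints. No aggregate tables are supplied either, so a finding that is missing from the listings is not picked up in a summary.

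What is at stake is narrow. An ECG abnormality reported as an adverse event reaches the DRC through the adverse event listings. An interval shift, or a change the investigator graded as not clinically significant, might not be reported as an adverse event. One such change in one patient may mean little. A similar change in several of the six active patients at one dose is what a dose-escalation review should be able to see, and nothing in the default package would show it.

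**Working it through.** The SAP states no figure on this point, so there is none to reproduce. The check has three parts.

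**1. Section 6.1 endpoints against the charter's Data Listings**

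| Section 6.1 group | Default DRC listing |
|---|---|
| Treatment-emergent adverse events | Adverse Events |
| Treatment-emergent serious adverse events | Serious Adverse Events |
| Laboratory changes (chemistry, hematology, urinalysis) | Labs, out-of-range values only |
| Vital signs | Vital Signs |
| Physical exams | Physical Exam |
| 12-lead ECG findings | none |

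Five of six groups are covered and one, ECG, is not.

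**2. Whether ECGs have been recorded by the time of the review**

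Screening and baseline ECGs are pre-dose. The 48-hour ECG is post-dose and falls well before the Week 6 visit (Day 42 ±8). Each patient therefore has one scheduled post-dose ECG with a pre-dose comparator before Week 6.

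**3. How many scheduled post-dose ECGs lie outside the default listings**

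Inputs: 8 patients per cohort and 3:1 randomization (section 3.1), so active patients per cohort = 8 × 3/4 = 6. All patients are assumed treated and tested.

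- First decision: 8 × 1 = 8 ECGs, of which 6 × 1 = 6 active.
- Second decision, data cut at each patient's Week 6: 2 × 8 = 16, of which 2 × 6 = 12 active.
- Second decision, data cut by database date: the charter's Administrative Data item describes the cutoff as everything entered by a given date. Cohort 2 cannot start before cohort 1 has been reviewed through Week 6. When the last cohort 2 patient reaches Week 6, cohort 1 is nominally at least 42 + 42 = 84 days past surgery, which is the Week 12 visit. Adding 8 Week 12 ECGs gives 16 + 8 = 24, of which 12 + 6 = 18 active.

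The last count is approximate because of the visit windows. With every visit at its early limit, the interval is 34 + 34 = 68 days, before the Week 12 window opens at 84 − 8 = 76. The DRC review and the enrollment of eight patients lengthen the interval in practice. ECGs at early termination or treatment failure could change any of these counts slightly.

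**The case against.** The strongest reply is that the charter does not make its list exclusive. It says these listings will be provided, not that no others will. The CRO's first duty in the charter is to supply the necessary data listings for each review meeting, with no approval condition, and the sponsor is charged with "Ensuring that the DRC has the information needed to execute its responsibilities". If escalation needs all available safety data, an ECG listing can be read as necessary. This shows that nothing bars the DRC from seeing ECGs. It does not close the gap, because neither duty names ECG and the specific list leaves it out.

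A reader might infer more: that the sponsor can keep ECG data from the DRC, because the CRO's duties also include "Providing additional information as requested by the DRC and approved by the Sponsor". The documents do not support that. The unconditional duty to provide necessary listings and the sponsor's own duty both point the other way, and nothing suggests that approval would be withheld. Whether that clause should be narrower is a matter of governance preference, not an error.

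A reader might also infer that the DRC decides with no cardiac information. That is too strong. Abnormalities reported as adverse events are listed, and the charter has the chair review serious events and events of special interest as they occur.

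Two further reservations stand. Section 5.3.4 keeps the traces at the sites, and section 8.10.3 does not say when interval values enter the database, so some may be missing at a review. The charter also predates Protocol Version 5.0 (27 July 2017), still carries a 24-week title where the SAP has 12 weeks of follow-up, and expects amendment. The mismatch may come from an attachment that was not updated, and a later version may exist that is not shown.

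**Conclusion.** The omission is real and minor. The charter's default listings cover every section 6.1 safety endpoint group except 12-lead ECG, so ECG changes not reported as adverse events have no stated default route into the escalation decision. The 16 and the 24 at the second decision depend on which cutoff is meant: section 3.1 can be read as a per-patient Week 6 cut, while the charter describes a database date.

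The conclusion rests on the charter shown being the one in force. It says nothing about the final analysis, which lists and summarizes ECGs in full, and it does not show that any safety signal was or would be missed.

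**What to change.** Add one item to the charter's Data Listings: 12-lead ECG, with intervals and investigator interpretation, for all pre-dose and post-dose records available at the cutoff. Worded this way, it works under either reading of the cutoff and includes Week 12 and early-termination ECGs where they exist.

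The cost is one more listing per DRC meeting. Section 8.10.3 already plans a by-subject ECG listing, so the programming can be shared. Interval values would need to be entered in time for each review.
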